## List Of Abbreviations And Relevant Definitions

ADA	Anti-drug antibody
AE	Adverse event
AUC 0-∞	Area under the concentration versus time curve extrapolated to infinity
Cmax	Maximum observed serum concentration
CL	Drug clearance
CV	Coefficient of variation
DMFA	Direct Membrane Feeding Assay
DSF	Direct Skin Feeding
DSMB	Data and Safety Monitoring Board
ELISA	Enzyme-Linked Immuno Sorbent Assay
GMT	Geometric mean titers
mAB	Monoclonal Antibody
PD	Pharmacodynamics
PK	Pharmacokinetics
SAE	Serious adverse event
SAP	Statistical analysis plan
SMFA	Standard Membrane Feeding Assay
SOP	Standard operating procedure
T 1/2	Terminal half-life
TBA	Transmission blocking activity
TRA	Transmission reducing activity
V d	Volume of Distribution

## Purpose

The purpose of the statistical analysis plan (SAP) is to outline the analyses that will be applied to the data generated in the described phase I/IIa trial, for the primary research outputs of this trial (i.e. the scientific paper/s reporting the primary and secondary outcomes). The SAP serves as a supplement to the protocol and contains further details about the study procedures to analyze the safety data, pharmacokinetics (PK) data and direct skin feeding (DSF), direct membrane feeding (DMFA) and standard membrane feeding assay (SMFA) data of participants of the trial.

The results reported in these papers should follow the strategy set out here. Subsequent analyses of a more exploratory nature will not be bound by this strategy, though they are expected to follow the broad principles laid down here. The principles are not intended to curtail exploratory analysis (for example, to decide cut-points for categorisation of continuous variables), nor to prohibit accepted practices (for example, data transformation prior to analysis), but they are intended to establish the rules that will be followed, as closely as possible, when analysing and reporting the trial.

The analysis strategy will be available on request when the principal papers are submitted for publication in a journal. Suggestions for subsequent analyses by journal editors or referees, will be considered carefully, and if reported will be carried out as far as possible in line with the principles of this analysis strategy and the source of the suggestion will be acknowledged.

Any deviations from the statistical analysis plan will be described and justified in the final report of the trial.

## Introduction

TB31F-Mali (full title 'A Phase 1/2a single centre, randomised, placebo-controlled, double-blind, dose escalation, age de-escalation, study to evaluate the safety, tolerability, pharmacokinetics, and *Plasmodium falciparum* transmission-reducing activity of monoclonal antibody TB31F in malaria-exposed Malian adults and children') is a Phase 1/2a single-centre, randomised, double-blind trial that aims to assess the safety and tolerability of monoclonal antibody (mAb) TB31F in Malian adults and school-age children, assess the pharmacokinetics of mAb TB31F in Malian adults and school-age children and assess the *P. falciparum* transmission reducing activity (TRA) of TB31F in naturally *P. falciparum* infected Malian individuals.

## Objectives

### Cohort 1: Safety

#### Primary objectives

- To assess the reactogenicity, tolerability, and safety of increasing doses of mAb TB31F in adults and school-age children
- To assess the population pharmacokinetics (pK) of a single subcutaneous injection of mAb TB31F in Malian adults and school-age children

#### Exploratory objectives

- To assess the impact of potential baseline and biochemical covariates on the population pharmacokinetics (pK) of a single sub-cutaneous injection of mAb TB31F in Malian school-age children
- To assess human genomic variation in the study population
- To assess the presence of plasma biomarkers in the study population

### Cohort 2: Efficacy

#### Primary efficacy objective

- To assess the transmission-blocking activity of mAb TB31F in serum as assessed in the Direct Membrane Feeding Assay (DMFA) at each dose level in naturally *P. falciparum* infected individuals

#### Primary safety/pharmacokinetics objectives

- To assess the reactogenicity, tolerability, and safety of increasing doses of mAb TB31F in Malian individuals
- To assess the population pharmacokinetics (PK) of a single sub-cutaneous injection of mAb TB31F in Malian individuals

#### Secondary efficacy objectives

- To assess the transmission-blocking activity of mAb TB31F assessed in the Direct Skin Feed (DSF) and DMFA at each dose level in naturally *P. falciparum* infected individuals
- To assess mosquito infection rate as measured by the proportion of dissected mosquitoes with any number of oocysts at each dose level in naturally *P. falciparum* infected individuals
- To assess the intensity of mosquito infection as measured by the average number of oocysts in dissected mosquitoes at each dose level in naturally *P. falciparum* infected individuals
- To assess participant infectivity after mAb TB31F administration at each dose level in naturally *P. falciparum* infected individuals

- To assess the transmission-reducing activity of participant serum after TB31F administration as assessed in the Standard Membrane Feeding Assay (SMFA) at each dose level in naturally *P. falciparum* infected adults and children

#### Exploratory objectives

- To develop an integral pharmacokinetic/pharmacodynamic (PK/PD) model describing the relationship between TB31F dose, time, individual characteristics, serum TB31F concentrations and SMFA and DSF/DMFA
- To assess the transmission-blocking activity of participant serum after TB31F administration as assessed in the Standard Membrane Feeding Assay (SMFA) at each dose level in Malian individuals
- To assess the quantitative relationship between SMFA, DSF, and DMFA results
- To assess the IC80 serum concentration after TB31F administration resulting in 80% transmission-blocking activity (TBA) in naturally *P. falciparum* infected individuals
- To assess the IC80 serum concentration after TB31F administration resulting in 80% transmission-reducing activity (TRA) in naturally *P. falciparum* infected individuals
- To assess the impact of naturally acquired TRA, present prior to TB31F administration, on transmission endpoints and TB31F efficacy estimates
- To assess human and parasite genomic variation and association with parasite measures
- To assess the impact of plasma biomarkers on malaria transmission efficiency

## Method

### Study design

The study is designed as a Phase 1/2a single-centre, double-blind, dose escalation, age de-escalation trial in malaria-exposed Malian adults and children. Two sequential stages of clinical research are conducted, each recruiting a distinct cohort of participants to confirm: 1. TB31F safety and 2. TB31F efficacy. Pharmacokinetic measurements will be performed in both safety and efficacy cohorts.

In total, a minimum of 165 participants will be recruited and enrolled; 45 adults and 30 children for the safety study, and ≥ 90 adults and children for the efficacy study. In the tables below, the cohorts are described with the number of participants, the duration of follow-up and the dose of TB31F administered.

*Table 1. Study design for Cohort 1 (Adults): Safety and pharmacokinetics (18-50 years of age)*

Group	Dose	N	Volume TB31F/Saline	Sample timepoints*	Safety follow-up after each dose administration
1	1A: Control (normal saline)	5	0.2 mL	Day 0 (Baseline), 1, 5, 7, 14, 21, 28, 42, 56, 84	Solicited local and systemic AEs (days 1-7); Unsolicited AEs (study duration); SAEs (study duration)
	1B: 10 mg mAb TB31F	10			
2	2A: Control (normal saline)	5	2 mL		
	2B: 100 mg mAb TB31F	10			
3	3A: Control (normal saline)	5	4 mL		
	3B: 200 mg mAb TB31F	10			

\* Group 1 participants will be followed-up until day 28

*Table 2. Study design for Cohort 1 (Children): Safety and pharmacokinetics in school age children (>10-15 years)*

Group	Dose	N	Volume TB31F/Saline	Sample timepoints	Safety follow-up after each dose administration
4	4A: Control (normal saline)	5	0.2 mL	Day 0 (Baseline), 1, 5, 7, 14, 21, 28, 42, 56, 84	Solicited local and systemic AEs (days 1-7); Unsolicited AEs (study duration); SAEs (study duration)
	4B: 10 mg mAb TB31F	10			
5	5A: Control (normal saline)	5	2.0 mL		
	5B: 100 mg mAb TB31F	10			

*Table 3. Study design for Cohort 2: Efficacy in a mixed age cohort (>10-50 years of age)*

Group	Dose	N	Volume TB31F/Saline	Sample timepoints	Safety follow-up after each dose administration
6.1	6AB: Control (normal saline)	15	0.6* mL	Day 0 (Baseline), 1, 5, 14, 21, 28, 56, 84	Solicited local and systemic AEs (days 1-7); Unsolicited AEs (study duration); SAEs (study duration)
	6B: 30 mg mAb TB31F	30	0.6* mL		
6.2	6AC: Control (normal saline)	15	2.0 mL		
	6C: 100 mg mAb TB31F	30	2.0 mL		

AE = Adverse events, SAE = Serious adverse events. Participants will be randomised in a 1:2:1:2 ratio to the 6AB, 6B, 6AC, or 6C group.

\* This dose will be informed by findings from the safety cohort and is expected to be ~30 mg; the volume will be adjusted accordingly.

## Randomization

Eligible participants will be assigned the next sequentially numbered study ID number based on a pre-printed Study ID List created by an independent statistician. Eligible participants will be randomised within each dose-group to either the control sub-group or the TB31F sub-group using a 1:2 ratio for Cohort 1 and Cohort 2. The randomisation codes will be provided to the study pharmacist. The study pharmacist in Mali will prepare the intervention for the study participants. For cohort 2, randomization will be performed in blocks of varying sizes.

## Sample size

The sample size is standard for the safety cohorts without formal sample size estimation. Sample size is informed by the anticipated efficacy from an earlier Phase I study and the transmission blocking effects observed in similar Malian cohorts when treated with transmission blocking drugs; this is done for the efficacy cohort only. This sample size for the efficacy cohort (n=30 per group) will give us 97% empirical power to detect >80% reduction in infectivity (defined as the percentage of mosquitoes with at least one oocyst) with a one-tailed test with a 0.025 level of significance when dissecting at least 40 mosquitos per participant at each timepoint. This power calculation is based on an online tool based on mixed effects logistic regression, an expected reduction in infectivity of 90%, an expected baseline proportion of infectivity of 15% for the average participant (accounting for non-infectious participants), and a conservative expected intra-cluster correlation of 0.5. Of note, this includes non-infectious individuals. In the four years that we performed NECTAR studies with a highly similar

study population, 66.0-79.5% of individuals infected at least one mosquito at enrolment with 14.2-17.0% of mosquitoes becoming infected. The power calculation given above includes all individuals (infectious and non-infectious). If we retain 30 individuals per arm and exclude those individuals who are not infectious at baseline ( $\leq 10$ ), the expected percentage of infected mosquitoes will increase from 15% (in the situation where some individuals infect no mosquitoes) to  $\sim 20\%$ . Based on a mixed effects logistic regression we looked at 200 simulations with an expected reduction in infectivity of 90%, an expected baseline proportion of infectivity of 20% for the average participant, and an expected intra-cluster correlation of 0.4. We estimated 91.5% empirical power to detect  $>80\%$  reduction in infectivity with a one-tailed test with a 0.025 level of significance when including 30 participants (of whom 20 are included in the analysis, i.e. after excluding non-infectious individuals) and dissecting 40 mosquitoes per participant at each timepoint. Importantly, these analyses are based on DMFA where venous blood is offered to mosquitoes. We and others have previously demonstrated that mosquito infection rates are at least 2-fold higher when allowing mosquitoes to feed directly on the skin of participants. When the expected baseline proportion infected mosquitoes is updated to account for higher infection rates by skin feeding (30% for the average participant) and we conservatively increase intra-cluster correlation to 0.8, we estimated 96% empirical power to detect  $>80\%$  reduction in infectivity with a one-tailed test with a 0.025 level of significance when including 30 participants and dissecting 40 mosquitoes per participant.

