### Efficacy outcome measures

#### **Efficacy outcome measures related to within-group % reduction in proportion infected mosquitoes:**

We will determine averaged within-individual percent reduction in the proportion of mosquitoes infected at days post-treatment (1, 5, 14) compared to baseline (day 0) for each group. This will be assessed through DMFA and DSF and outcomes for these different feeding assays will be presented separately as percentage reduction (with 100% as total reduction of transmission, and negative values as enhanced transmission) with 95% confidence interval. Data will be analysed for all individuals who received the product per protocol and only for those individuals who are infectious at baseline (i.e. infecting at least one mosquito with any number of oocysts). All analyses on within-individual percentage reduction in the proportion of infected mosquitoes will use a mixed effects generalized linear model assuming a binomial error structure and a log-link, using individual mosquito data with day of follow-up and dose of TB31F and their interaction as fixed effects. A random intercept will be added to models to allow for participant-level variation in pre-intervention transmissibility and thus account for the correlation between outcomes for mosquito samples from the same participant (i.e. intra-cluster correlation).

In exploratory analyses, these analyses will be performed following stratification for naturally acquired transmission reducing immunity, as quantified by SMFA at baseline (pre-TB31F administration) samples.

The impact of naturally acquired transmission reducing immunity, assessed in baseline samples by SMFA (TRA>50%; TRA>80%) and by antibody prevalence to known gamete antigens Pfs230 and Pfs48/45, on infecting mosquitoes will also be determined. For this, TRA as categorical variable and antibody prevalence (binary variable), will be added as fixed effects to mixed effects logistic regression models on proportion infected mosquitoes at baseline (pre-TB31F administration). These models may be expanded to include human genetic factors (e.g. a fixed effect for HbAS or HbAC carriage as compared to wild-type HbAA).

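### The 97% power for the membrane-feeding endpoint is too high: at the SAP's own average infection rate of 15% it is about 85-90%

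*SAP*

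**What the plan says.** The SAP's Sample size section says that 30 participants per group, with at least 40 mosquitoes dissected per participant and timepoint, "will give us 97% empirical power to detect >80% reduction in infectivity (defined as the percentage of mosquitoes with at least one oocyst"). The test is one-tailed at 0.025, the expected true reduction is 90%, and the intra-cluster correlation (ICC) is 0.5. The baseline input is "an expected baseline proportion of infectivity of 15% for the average participant (accounting for non-infectious participants"). On method: "This power calculation is based on an online tool based on mixed effects logistic regression".

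The same section supports the 15% with earlier studies in a similar population, where "66.0-79.5% of individuals infected at least one mosquito at enrolment with 14.2-17.0% of mosquitoes becoming infected". It then removes people who are not infectious at baseline and says that "the expected percentage of infected mosquitoes will increase from 15% (in the situation where some individuals infect no mosquitoes) to" about 20%. A second calculation uses 20 analysed participants, ICC 0.4 and "an expected baseline proportion of infectivity of 20% for the average participant": "We estimated 91.5% empirical power to detect" a reduction above 80%, from 200 simulations. A third, for skin feeding (30%, ICC 0.8), gives 96%.

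The planned analysis of the within-individual reduction (Efficacy outcome measures, first subsection) is a "mixed effects generalized linear model assuming a binomial error structure and a log-link", with a participant random intercept.

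**The concern.** In a logistic model with a random intercept, a baseline proportion can mean two things: the average over all participants, or the rate of the participant whose random effect is zero. With large variation between participants these are far apart. The SAP's wording for the 15% could suggest the second. Its evidence is of the first kind: a percentage of mosquitoes infected, counting people who infect none, which rises when those people are removed (15%/0.75 = 20%). The SAP does not say which was entered, on which scale the ICC is defined, or which test was simulated.

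The figure concerns the primary efficacy measure, the day 5 membrane-feeding (DMFA) reduction. If a dose level fails to show a reduction above 80%, a reader who trusts 97% will take that as near-conclusive evidence that the true reduction is below 90%. At the lower power it is weaker evidence.

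**Working it through.** **Inputs (SAP, Sample size).** n = 30; 40 mosquitoes per participant at baseline and post-dose; baseline 15%; ICC 0.5; true reduction 90% against a null of 80%; one-sided 0.025.

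**Assumption.** The ICC is on the latent logit scale, so the random-intercept variance is ICC/(1−ICC) × π²/3. At 0.5 this is 3.29, an SD of 1.81.

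**Step 1: reproduce the 97%.** Enter 15% as the rate at random effect zero. The logistic mixed model gives 97.4-98.1% (Wald) and 97.9-98.4% (likelihood ratio). The 20-participant case (20%, ICC 0.4) gives about 93-95% on the same reading, against the stated 91.5%.

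**Step 2: compare each reading with the SAP's own data.**

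| | Mosquitoes infected at baseline | Participants infecting none of 40 |
|---|---|---|
| SAP's earlier studies | 14.2-17.0% | 20.5-34.0% (100 minus 79.5 and 66.0) |
| 15% at random effect zero | 24.4% | 12.4% |
| 15% as group average | 15.0% | 23.0% |

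The group-average reading fits both rows of evidence, and the other reading fits neither. With a 15% average, the rate at random effect zero is 6.9%.

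**Step 3: power at a 15% group average.** In the log-scale rows each participant's post-dose rate is 0.1 times the baseline rate. In the logistic rows the odds ratio is 0.1 against a null of 0.2. Size is the rejection rate at a true 80% reduction.

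| Test | Power | One-sided size |
|---|---|---|
| Exact conditional binomial (null probability 0.2/1.2 = 1/6) | 85% | 1.5% |
| Log ratio, robust SE | 87% | 3.4% |
| Log-link mixed model, Wald | 87% | 2.0% |
| Log-link mixed model, likelihood ratio | 90% | 2.7% |
| Logistic mixed model, Wald | 88% | not tabulated |
| Logistic mixed model, likelihood ratio | 90% | not tabulated |
| Untransformed percent reduction | 94% | 5.7% |

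**Step 4: sensitivity.** Exact, robust log, log-link Wald and log-link likelihood ratio, in that order:
- at 14.2%: 83.0, 85.3, 86.0 and 89.5%;
- at 17.0%: 89.7, 91.0, 92.0 and 94.1%.

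These tests reach 97% only at an average of about 21-23%. The result hardly depends on the ICC: at 15%, ICC 0.45 and 0.68 give 85.4% and 84.1% (exact), and 87.3% and 87.1% (robust log). Modelling 20.5-34% of participants as never infectious gives 85-87% (log-ratio tests).

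**Step 5: crude hand check, independent mosquitoes.** Each timepoint has 30 × 40 = 1,200 mosquitoes, so 180 and 18 infected are expected. The SE of the log ratio is √(1/180 + 1/18 − 2/1,200) = 0.244. Power ≈ Φ(ln 2/0.244 − 1.96) = Φ(0.88) = 81%. This ignores the pairing and the skewness, but it is nowhere near 97%.

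**Step 6: the other two figures.**
- *20 participants.* At an average of exactly 20%, power is 81-87% against 91.5%. If 20 remain at 15% × 30/20 = 22.5%, it is 86-91%. Drawing 30 at an average of 15% and dropping the non-infectious leaves about 23 at 19.5%, and power is 88-93%.
- *Skin feeding.* At an average of 30% and ICC 0.8, power is about 96% in the logistic model and about 99% with log-scale tests. The stated 96% is not too high.

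**The case against.** The strongest objection is that the cause of the 97% cannot be settled. Entry at random effect zero fits the two DMFA figures, but it fits skin feeding less well: in the logistic model it gives 98.5%, while group-average entry gives 95.9% against the stated 96%. The untransformed test offers another route: with group averages it gives 94% for the first figure and 92% for the second. If the 97% also came from 200 simulations, its exact 95% interval is 93.6-98.9%, which just includes 94%. This stands as a caution about the mechanism. It does not rescue the figure, because 94% is still short of 97% and that test has more than twice its nominal size.

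Read literally, a rate for the average participant can mean random effect zero, and then 97% follows from the input. That is fair, and the fault is then in the input: data with about 15% of mosquitoes infected put that participant near 7%.

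Three smaller points also stand. The 85% end comes from a conservative exact test that the SAP does not name; the SAP's own model types give 87-90%. Forty mosquitoes is a minimum. Power stays above 80% in all the main tests, so the design is not undermined.

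**Conclusion.** The concern holds. At a 15% group average, the DMFA design has about 85-90% power (87-90% with the SAP's own types of model), not 97%. Over 14.2-17.0% the range is 83-94%. The risk of missing a true 90% reduction at one dose level is about 10-15%, three to five times the 3% implied. The 91.5% for infectious participants only is probably optimistic, but it depends on how many remain and at what rate. No overstatement is claimed for skin feeding.

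The result rests on normally distributed participant effects on the logit scale and on a latent-scale ICC; the latter matters little to the corrected figures. The explanation of how the 97% arose remains an inference.

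**What to change.** In the Sample size section:
- state that 15% and 20% are group-average proportions of infected mosquitoes, and give the scale of the ICC;
- re-run both DMFA simulations on that basis with the planned log-link mixed model and a named test, and report that test's type I error at a true 80% reduction;
- replace 97% and 91.5% with the values obtained;
- re-run the skin-feeding figure in the same way, so that all three are comparable.

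The cost is one simulation run and a few sentences. Enrolment and the analysis do not change; the only drawback is a less favourable stated power.

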#### Statistical interim analyses and stopping guidance

There are no pre-defined criteria for study termination in this clinical trial but safety and reactogenicity data will be evaluated after each mAb TB31F administration before proceeding to the next group. A safety report including a list of all reported adverse events and any clinically significant safety laboratory values outside the normal ranges will be prepared:

- After completion of day 14 follow-up after IP administration from groups 1-2 AND before start of groups 3 and 4.
- After completion of day 14 follow-up after IP administration from group 3-4 AND before start of group 5.
- After completion of day 7 follow-up after IP administration from group 5 AND before start of group 6.
- Upon completion of the study.

#### Statistical Software

- Safety data analysis will be performed in STATA (latest version available), or R.
- SMFA, DMFA and DSF data analysis will be performed in R.
- The pharmacokinetic and pharmacokinetic/pharmacodynamic analyses will be performed by means of compartmental non-linear mixed effects modelling, using the software package NONMEM V7.5 (Icon, Dublin, Ireland) using R and the Perl modules package Perl Speaks NONMEM v5.4.0 for data processing.

